## **Collection and Recording of Adverse Events**

### Collection Period

Serious adverse events will be collected from the time of first dose of study medication until a participant completes study participation, or until 30 days after the participant prematurely withdraws (without withdrawing consent) or is withdrawn from the study. Grade 3 or higher AEs will be reviewed by the investigator and will be reported if they are possibly or definitely related to the study medication.

### Collecting Adverse Events

Adverse events (including SAEs) may be discovered through any of these methods:

1. Observing the participant
2. Interviewing the participant [e.g., using a checklist, structured questioning, diary, etc.]
3. Receiving an unsolicited complaint from the participant
4. In addition, an abnormal value or result from a clinical or laboratory evaluation can also indicate an adverse event, as defined in Section 2.9.3, Grading and Attribution of Adverse Events

### Recording Adverse Events

Throughout the study, the investigator will review all grade 3 or higher AEs and if potentially related to a study medication, will report them to the IRB. All SAEs will be reported to the IRB.

Once reported, an AE/SAE will be followed until it resolves with or without sequelae, or until the end of study participation, or until 30 days after the participant prematurely withdraws (without withdrawing consent) or is withdrawn from the study, whichever occurs first.

## **Reporting of Serious Adverse Events and Adverse Events**

Adverse Events and Serious Adverse Events Exempt from Reporting:

1. Any AE lower than grade 3

## **Reporting of Other Safety Information**

An investigator shall promptly notify the site IRB when an “unanticipated problem involving risks to participants or others” is identified, which is not otherwise reportable as an adverse event

## **5. Inclusion/Exclusion Criteria**

### Recipient Inclusion Criteria

1. Participants  $\geq$  18 years old
2. On the deceased donor kidney waitlist at Johns Hopkins Hospital
3. Awaiting a first or second kidney transplant
4. No cleared living kidney donors

Date: September 26, 2023

Principal Investigator: [name]

Application Number: IRB00237097

5. On hemodialysis or peritoneal dialysis or stage 5 CKD defined as a glomerular filtration rate <15 ml/min for  $\geq$  past 90 days
6. HCV- nonviremic (by HCV RNA PCR) and without any behavioral risk factors for contracting HCV other than being on hemodialysis
7. Calculated panel reactive anti-HLA antibody (flow cPRA) below 80%

#### Recipient Exclusion Criteria

1. Plan to receive a multi-organ transplant
2. Plan to receive a dual kidney transplant (including en bloc)
3. Participating in another study that involves an intervention or investigational product
4. Plan to receive a blood type incompatible kidney
5. History of human immunodeficiency (HIV), hepatitis C (HCV), or active hepatitis B (HBV) infection, defined as being on active antiviral treatment for HBV, detectable hepatitis B surface Ag or detectable hepatitis B DNA
6. Unable to safely substitute or discontinue a medication that is contraindicated with the study medication
7. Psychiatric or physical illness that in the opinion of the investigator would make it unsafe to proceed with transplantation or interfere with the ability of the subject to participate in the study

#### Donor Inclusion Criteria

1. Donor age 13-60 years
2. Donation after brain death or donation after cardiac death donor
3. Projected cold ischemia time of 40 hours or less
4. Terminal creatinine less than 10.0 mg/dL
5. No evidence of significant chronic pathologic findings on pre-implantation biopsy
6. HCV positive by nucleic acid (RNA) testing

### **6. Drugs/ Substances/ Devices**

Co-formulated glecaprevir 300 mg/pibrentasvir 120 mg will be provided by the study, dispensed from the Investigational Drug Service (IDS). The G-P orally will be initiated on call to the operating room for kidney transplantation. Dosing will continue every 24 hours postoperatively through week 2 after transplantation for donors with any genotype of HCV (genotypes 1-6).

#### Rescue Treatment

With the availability of a pan-genotypic HCV medication that is safe to use with renal dysfunction, we expect all recipients to be adequately treated with G-P. However, we will perform genotyping on the donor blood sample in order to help guide therapy if there is a treatment failure. Based on the results of our initial studies using this strategy (EXPANDER, REHANNA), we expect 70 percent of donors to have genotype 1 and the other 30% to be have genotype 2 or 3.

If a treatment failure were to occur, recipient genotype and mutation analysis would be performed and the most recent AASLD/IDSA HCV treatment guidelines ([hcvguidelines.org](http://hcvguidelines.org)) would be followed to select the most appropriate regimen to use in any cases of HCV infection. This would be considered clinical care.

### **7. Study Statistics**

Date: September 26, 2023

Principal Investigator: [name]

Application Number: IRB00237097

**A. Primary Outcome Variable:**

- The primary outcome will be the proportion of kidney transplant recipients with undetectable plasma HCV RNA at 12 weeks after stopping treatment.

**B. Secondary Outcome Variables:**

- Detection of HCV antibodies
- Allograft function at 6 and 12 months
- If there are transplant recipients with detectable plasma HCV RNA after treatment or if there is viral breakthrough on treatment, we will measure prevalence of NS3 and NS5A mutations in HCV from the recipient plasma. Mutation testing will be guided by the HCV genotype that is present.

**C. Statistical plan including sample size justification and interim data analysis:**

The Johns Hopkins group will be responsible for collecting data, maintaining the database, and data analysis. Both our transplant surgery and transplant infectious disease group have extensive experience leading hepatitis C treatment studies and multicenter NIH-funded studies examining outcomes in transplant.

Our Transplant Infectious Disease Group has an active prospective database collecting outcomes, including infectious complications, on the JH cohort of all solid organ transplant recipients. The cohort design facilitates use of standardized outcomes definitions, prospective capture of event-driven data, and collection of information after discharge from the referral center. Expanding on these existing protocols and infrastructure, we will leverage infrastructure and resources from the Department of Surgery clinical research unit and the JH Comprehensive Transplant Center (CTC) for the planned study. Moreover, the JH Transplant and Oncology Infectious Diseases Clinical Research Coordinating Center (Infectious Diseases) has committed support for document development and regulatory support. These groups have staff dedicated to regulatory oversight and development and compliance with reporting requirements and we have successfully collaborated already in generating the preliminary data shown above.

**Data Collection Mechanism:**

Data collection will be performed using the REDCap electronic data collection and storage hosted by Johns Hopkins University. All data in REDCap will be de-identified. Each site will maintain a record of which subject corresponds to subject numbers assigned by REDCap. This file will be password protected if electronic or kept in a locked location if in the subject binder.

In brief, the REDCap Consortium consists of 84 institutional partners from CTSA, GCRC, RCMI and other institutions, in which JH is an active participant. It was developed by CTSA partners at Vanderbilt, with the goal of enabling investigator research through the establishment of a more user-friendly database system. This consortium supports two secure web-based applications designed to enable data capture for research studies. The software contains an intuitive interface for collecting data with data validation commands, allows for automated export procedures to statistical packages (e.g. SAS) and provides advanced features that allow for branching logic, file uploading, etc. The system itself is supported on MySQL, an open source database similar to SQL/Oracle, and operates on a web-based system. All servers are backed-up at each data center (institution) and include password protection to provide enhanced security while maintaining accessibility via the internet.

Date: September 26, 2023

Principal Investigator: [name]

[figure not shown]
Application Number: IRB00237097

**Data Monitoring:**

Upon enrollment of subjects, the REDCap database constructs a calendar of anticipated events, which includes completion of follow-up case report forms, with electronic reminders

**Power/Sample Size:**

**Figure 4.** We hypothesize that the treatment strategy will be 100% effective and that the HCV RNA<LLOQ in all 10 patients. Given that this is a pilot study with no comparison group, the power to detect a difference depends on the true efficacy. For example, if the true efficacy is 79%, then we will have at least one observed outcome 90.53% of the time ( $1-0.79^{10}$ ). Figure 4 demonstrates the relationship between the true efficacy and the power of the proposed study.

## 8. Risks

### A. Medical Risks:

Although it has not been reported, due to acute infection with hepatitis C, there is a slight risk of acquiring hepatitis C, fulminant hepatitis, and death.

**Glecaprevir/Pibrentasvir:**

The most common side effects with these drugs are nausea, headache, and fatigue.

**Blood Draw:**

Taking blood may cause discomfort, bleeding or bruising where the needle enters the body. In rare cases, it may result in fainting. There is a small risk of infection.

Pregnancy: To date there is no adequate human data available to establish whether or not the study drug poses a risk to an embryo or fetus. To ensure patient safety, study treatment must be discontinued and the subject withdrawn if pregnancy occurs while the patient is on study treatment. Women, and men with female partners capable of becoming pregnant, must use effective methods of birth control.

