#### **2. Objectives**

##### Primary objectives:

The primary objectives of this study are to evaluate the safety and efficacy of glecaprevir 300 mg/pibrentasvir 120 mg (G-P) treatment in HCV-nonviremic transplant recipients (HCV R-) of a kidney from an HCV-infected deceased donor (HCV D+). G-P will be administered on-call to the operating room (OR) for the kidney transplant procedure and continued for 2 weeks after the kidney transplant.

- The primary efficacy outcome will be the proportion of HCV D+/R- renal transplant recipients with undetectable HCV plasma RNA at 12 weeks after treatment (14 weeks after kidney transplant).
- The primary safety outcome will be the incidence of adverse events (AE) related to G-P.

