#### Serious Adverse Event (SAE) Definition

An adverse event or suspected adverse reaction is considered “serious” if, in the view of the investigator it results in any of the following outcomes (21 CFR 312.32(a)):

1. Death
2. A life-threatening event: An AE or SAR is considered “life-threatening” if, in the view of the investigator, its occurrence places the participant at immediate risk of death. It does not include an AE or SAR that, had it occurred in a more severe form, might have caused death.
3. Inpatient hospitalization or prolongation of existing hospitalization
4. Persistent or significant incapacity or substantial disruption of the ability to conduct normal life functions
5. Congenital anomaly or birth defect
6. Important medical events that may not result in death, be life threatening, or require hospitalization may be considered serious when, based upon appropriate medical judgment, they may jeopardize the participant and may require medical or surgical intervention to prevent one of the outcomes listed above

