**Pregnancy:**

**Women only:**

Women who can get pregnant should not take study drug(s) unless they and their partner do not have intercourse ever or are using 2 methods of birth control for the duration of the study (starting 3 weeks prior to the Day 1 visit) and for a minimum of 6 months after last dose of study drug or longer as directed by your study doctor.

At least one method of birth control must be a condom.

Women who can get pregnant must have a negative pregnancy test at time of admission for transplant, and prior to taking the first dose of study drug.

Female subjects must notify the study team if they become pregnant while in this study and for 6 months after stopping the study drug, or for as long as directed by the study doctor to use contraception. In the event of a positive urine pregnancy result, subjects will be instructed to return to the study clinic as soon as possible for a serum (blood) pregnancy test.

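### Pregnancy on G-P triggers study withdrawal as well as treatment stop, leaving HCV RNA follow-up to the 12-week endpoint unassured and any birth outcome outside the SAE window

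*Combined protocol and SAP*

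**What the plan says.** Section 8.A (Medical Risks), in the Pregnancy text printed under Blood Draw, states that "study treatment must be discontinued and the subject withdrawn if pregnancy occurs while the patient is on study treatment". Stopping the drug and withdrawing the subject are two actions in that sentence. The protocol does not define what withdrawal entails.

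Section 4, Collection Period, gathers SAEs from the first dose until participation is complete, or "until 30 days after the participant prematurely withdraws (without withdrawing consent) or is withdrawn from the study". Recording Adverse Events (section 4, repeated in section 8.C) adds: "Once reported, an AE/SAE will be followed until it resolves with or without sequelae, or until the end of study participation". The same 30-day limit is the third stopping point there, and the earliest of the three applies.

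The SAE definition in section 4 includes "Congenital anomaly or birth defect". Section 8.B, Women only, says: "Female subjects must notify the study team if they become pregnant while in this study and for 6 months after stopping the study drug". It also says that women who can conceive "must have a negative pregnancy test at time of admission for transplant", and it describes a confirmatory serum test after a positive urine result. It does not mention collecting the outcome of a pregnancy.

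Section 2 places the primary efficacy outcome 12 weeks after treatment, which is 14 weeks after transplant. The Visit Schedule in section 4 lists follow-up weeks (FW) 1, 2, 4 and 12 for all participants, without saying whether that covers someone who has been withdrawn.

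**The concern.** A treatment stop and a study exit serve different purposes, and here one event triggers both. The participant keeps a kidney from a donor who had to be HCV RNA positive (section 5, Donor Inclusion Criteria). If the pregnancy is recognised during dosing, she has also received less than the two-week course under test. Her result at 12 weeks is therefore of particular interest, yet nothing in the protocol secures it once she is withdrawn.

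The safety side has the same shape. Section 8.A says that human data on fetal risk are inadequate, and the SAE definition names one fetal outcome. The withdrawal clause then starts a 30-day clock that runs out long before a birth would be expected.

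At stake are one of ten primary endpoints and the only fetal SAE that the protocol defines.

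**Working it through.** **1. The plan's own figure.** Power/Sample Size (section 7) gives the chance of at least one failure among 10 when true efficacy is 79%: 1 − 0.79^10 = 0.9053. This reproduces the stated 90.53% and is not in dispute. With nine evaluable participants it is 1 − 0.79^9 = 0.8801.

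**2. SAE window against the endpoint.** Inputs: dosing through week 2, about day 14 (section 6); a 30-day window (Collection Period); an endpoint at 12 weeks = 84 days after treatment (section 2). Assume that withdrawal falls on the day the drug is stopped.
- Stop on day 1: SAE collection ends on day 1 + 30 = 31; FW 12 would be day 1 + 84 = 85.
- Stop on day 14: SAE collection ends on day 14 + 30 = 44; FW 12 would be day 14 + 84 = 98.
- The gap is 84 − 30 = 54 days either way.

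**3. SAE window against a birth.** The documents give no time from conception to birth. Assume 22 to 38 weeks, very preterm to term.
- Conception on day 0 to day 14 puts birth at study week 22 to 2 + 38 = 40.
- Withdrawal by day 14 closes collection by day 44 (week 6.3).
- If the pregnancy is recognised and acted on later, the window moves with it. To reach even the earliest assumed birth (22 × 7 = day 154), withdrawal would have to be on day 154 − 30 = 124 or later.
- A woman who stayed in would be covered until she completed participation. If that is one year, as Year 2 Long-Term Follow-Up (section 4) suggests, weeks 22 to 40 fall inside. The loss then comes from the withdrawal clause itself.
- The notification duty runs to about (14 + 182.6)/7 = week 28. It concerns becoming pregnant, not how the pregnancy ends.

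**4. One lost endpoint at n = 10** (exact Clopper-Pearson 95% intervals).

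| Handling | Result | Interval |
|---|---|---|
| All ten observed, all successes | 10/10 | 69.2% to 100% |
| Lost participant excluded | 9/9 | 66.4% to 100% |
| Lost participant counted as failure | 9/10 | 55.5% to 99.7% |

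For all successes the lower limit is 0.025^(1/n): 0.025^(1/10) = 0.692 and 0.025^(1/9) = 0.664.

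**5. Testing a replacement window.** A flat limit of 12 weeks after the last dose would shorten collection for anyone withdrawn more than 84 − 30 = 54 days after that dose. Withdrawal 10 weeks after the last dose gives 70 + 30 = 100 days now but only 84 under the flat limit. Taking the later of the two dates gives 100 there, and 84 for someone withdrawn on the day of the last dose, so nobody loses coverage. Twelve weeks still does not reach a birth, so the pregnancy outcome needs its own rule.

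**The case against.** The strongest reply is that nobody was affected. Year 2 Long-Term Follow-Up records that by August 18, 2022 all 10 subjects had been accrued and had completed the 1-year study. What remains is chart review. That stands, and it rules out any claim that this trial's success proportion is biased. A reader might infer upward bias, but the documents show no lost participant and state no denominator rule. Counting a lost participant as a failure would push the estimate down.

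The event is also rare. It needs a pregnancy within about 14 days of dosing, after a negative test at admission and with two contraceptive methods required from 3 weeks before Day 1. Prophylaxis is shortened only if the pregnancy is recognised during those days. A pregnancy that begins after treatment does not trigger withdrawal at all. This stands too.

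Next, loss of the RNA visits is an inference. Withdrawal is undefined, the visits are listed for all participants, and the consent pages, which might carry follow-up terms, were not available for this review. That limits the finding to follow-up that is not assured, rather than follow-up that is certainly lost.

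A reader might also say that the sections contradict one another. They do not: the SAE definition sets seriousness, not a collection window, and the notification duty is separate from SAE collection. They are unreconciled. Nor does the lack of a pregnancy test in Table 1 prove a conflict with section 8.B. That table also omits the admission test and the later graft-function assessments, and a positive urine result could come from elsewhere.

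Finally, routine chemistry, clinical care of treatment failure (section 6), the centre's prospective transplant database (section 7) and reporting of unanticipated problems could bring a hepatitis or a birth defect to light. None of them commits the study to a 12-week RNA result or to a recorded pregnancy outcome, so the gap remains.

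**Conclusion.** The concern holds as a gap in the protocol's wording. Followed literally, the withdrawal clause and the 30-day limit leave the 12-week RNA endpoint unassured and put a birth outcome beyond SAE collection. The SAE window closes 54 days before the endpoint if withdrawal coincides with stopping the drug. It closes by day 44 for withdrawal during dosing, against an assumed birth at study week 22 to 40.

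One such loss would move the lower confidence limit from 69.2% to 66.4% or 55.5%, depending on a handling rule that section 7 does not give. These limits assume that the other nine succeed.

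The conclusion rests on reading withdrawal as an exit from study follow-up, and on the assumed 22 to 38 weeks from conception to birth. It does not show that a result was distorted or that hepatitis was missed, and the documents give no figure for HCV risk after a shortened course. The correction is worth making if the protocol is amended or reused. It does not change the interpretation of this cohort.

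**What to change.** Leave the treatment-stopping rule as it is and change the data collection around it.

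- **Section 8.A, Pregnancy.** Reword so that stopping G-P does not end study participation. State that a participant who still consents stays in the Table 1 RNA and chemistry follow-up, and in SAE follow-up, through FW 12.
- **Collection Period and both copies of Recording Adverse Events.** For withdrawal without withdrawn consent, replace the 30-day limit with *the later of 30 days after withdrawal or 12 weeks after the last dose*.
- **Pregnancy outcome.** For any pregnancy reported under section 8.A or 8.B, record the outcome with consent, including any congenital anomaly.
- **Reconciliation.** The sponsor should bring the SAE definition, the Collection Period and the pregnancy text in sections 8.A and 8.B into line with one another.

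The cost is protocol wording, a few follow-up contacts and blood draws that Table 1 already schedules for the rare participant affected, and one outcome call per pregnancy.

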### B. Steps taken to minimize the risks:

**Medication Side Effects:**

Date: September 26, 2023

Principal Investigator: [name]

Application Number: IRB00237097

Participants will be monitored closely and instructed to report any change in their medical condition promptly. Side effects will be assessed and managed as clinically indicated.

**Blood Draw:**

Only properly trained clinical staff will draw blood. The amount of blood collected is the minimal amount for proper analysis.

**Pregnancy:**

**Women only:**

Women who can get pregnant should not take study drug(s) unless they and their partner do not have intercourse ever or are using 2 methods of birth control for the duration of the study (starting 3 weeks prior to the Day 1 visit) and for a minimum of 6 months after last dose of study drug or longer as directed by your study doctor.

At least one method of birth control must be a condom.

Women who can get pregnant must have a negative pregnancy test at time of admission for transplant, and prior to taking the first dose of study drug.

Female subjects must notify the study team if they become pregnant while in this study and for 6 months after stopping the study drug, or for as long as directed by the study doctor to use contraception. In the event of a positive urine pregnancy result, subjects will be instructed to return to the study clinic as soon as possible for a serum (blood) pregnancy test.

**Men only:**

If male subjects have a female partner who cannot become pregnant, they must still consistently and correctly use a condom.

If male subjects have a female partner who can become pregnant, subject must use two forms of birth control for the entire study and for a minimum of 6 months after the last dose of study drug.

Male participants must also agree not to donate sperm from the time of first dose of study drug until 6 months after the last dose of study drug.

